1.0 Investigational Design

1.1.Study Design

This investigation is a randomized controlled trial of three techniques to evaluate clinically, radiographic, and histologically the efficacy of L-PRF with freeze-dried bone allograft (FDBA) layered technique in improving quantity and quality of new vital bone formation and alveolar ridge dimensional stability following ridge preservation in comparison to L-PRF alone and L-PRF/FDBA.

Control technique: Ridge preservation using L-PRF/FDBA and ridge preservation using L-PRF alone

Test technique: Ridge preservation using L-PRF/FDBA layered technique

1.2. Objectives:

- To evaluate clinical and radiographic dimensional changes at alveolar ridge 3 months after ridge preservation procedure using L-PRF alone, L-PRF/FDBA, and L-PRF/FDBA Layered technique.

- To evaluate quantity and quality of new vital bone in sockets 3 months after ridge preservation procedure using L-PRF alone, L-PRF/FDBA, and L-PRF/FDBA Layered technique.

1.3. Hypotheses and Specific Aims:

- **Hypothesis 1:** Ridge preservation using L-PRF/FDBA Layered technique will best preserve alveolar ridge dimensions in comparison to using L-PRF alone.
- **Hypothesis 2:** Ridge preservation using L-PRF/FDBA Layered technique will improve new vital bone formation at the middle and apical thirds of the socket in comparison to using L-PRF/FDBA.

• Specific Aims:

1. To compare quantitative clinical alveolar ridge dimensions (in mm) 3 months after ridge preservation between the three groups using an intraoral scan and direct clinical assessment.

- 2. To compare quantitative two- and three- dimensional radiographic alveolar ridge dimensional changes (in mm) 3 months after ridge preservation between the three groups using Cone Beam Computed Tomography (CBCT) and virtual implant planning software.
- 3. To compare qualitative and quantitative histologic characteristics of new bone between the three groups after 3 months of ridge preservation by quantifying the distribution (in %) of new vital bone, connective tissue, residual graft particles, and artifact at the healed socket site.

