A power analysis was conducted to determine the sufficient number of patients in each treatment group to obtain a power of 80% to detect a 1.0mm change in ridge dimensions using a type 1 (alpha) error rate of 0.05. The power analysis determined that a minimum of 10 patients would be required for each group, and 30 patients in total. An alpha of 0.05 was assumed after a Bonferroni correction for five relevant 2-way comparisons between the treatment groups.

Two-tailed *t* test will be used to compare clinical characteristics between patients with the L-PRF/FDBA layered technique, L-PRF/FDBA, and those with L-PRF alone for continuous variables with a normal distribution. Nonparametric (Wilcoxon) test will be used otherwise.

For categorical variables, inter-group comparisons will be conducted using chi-square test or Fisher's Extract Test, as deemed necessary. To determine whether the groups experienced equivalent changes in bone growth from baseline to follow-up, paired *t* (or Wilcoxon signed-rank) and Mc Nemar's tests will be used for continuous and categorical variables, respectively.

The α level will be set at 0.05. Statistical analysis will be carried out using SAS software version 9.4 (SAS Institute, Inc, Cary, North Carolina).

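### The plan answers whether the three groups changed alike with within-patient paired tests and assigns no between-group test to change

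*Combined protocol and SAP*

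**What the plan says.** All the analysis text is in section 3.4 of the combined protocol and SAP.

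- **Change.** The sentence on change opens "To determine whether the groups experienced equivalent changes in bone growth from baseline to follow-up, paired" and goes on to name the paired t test (or Wilcoxon signed-rank) for continuous variables and McNemar's test for categorical ones.
- **Between-group, continuous.** A two-tailed t "test will be used to compare clinical characteristics between patients with the L-PRF/FDBA layered technique, L-PRF/FDBA, and those with L-PRF alone", for normally distributed continuous variables. "Nonparametric (Wilcoxon) test will be used otherwise". Change is not mentioned.
- **Between-group, categorical.** For these, "inter-group comparisons will be conducted using chi-square test" or Fisher's test. Change is not mentioned.
- **Power.** The trial is sized "to detect a 1.0mm change in ridge dimensions using a type 1 (alpha) error rate of 0.05", with 80% power and 10 patients per group. The paragraph adds: "An alpha of 0.05 was assumed after a Bonferroni correction for five relevant 2-way comparisons between the treatment groups". It names no test.

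Section 1.3 sets the questions. Aim 2 compares "radiographic alveolar ridge dimensional changes (in mm) 3 months after ridge preservation between the three groups". Aim 1 is worded as a comparison of dimensions: "To compare quantitative clinical alveolar ridge dimensions (in mm) 3 months after ridge preservation between the three groups". Hypothesis 1 sets the layered technique against L-PRF alone on preservation of the ridge.

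**The concern.** The question is about differences between groups, while the tests named for it work within patients. A paired t, signed-rank or McNemar test on one group asks only whether that group changed.

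An analyst following the sentence as written would set three within-group p-values side by side and read the answer from which are significant. That reading fails both ways. One significant and one non-significant result do not show that two groups differ, and two significant results do not show that they are alike. The sentence also speaks of equivalence, but no margin is set anywhere.

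Aim 2 is most directly affected. If the unpaired test was in fact meant for change, the plan does not say so, and the choice of analysis stays open until the data are seen.

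**Working it through.** **1. Which outcomes the sentence can cover.** It refers to bone growth from baseline to follow-up. The bone biopsy is taken once, at 3 months (section 3.1, Visit 4; Table 2), so histology has no baseline. The bone measurements planned at both times are the clinical and radiographic ridge dimensions (section 3.3). The sentence therefore governs ridge change.

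**2. Is there a between-group test of change elsewhere?** Section 3.4 contains no ANOVA, ANCOVA, mixed model or group-by-time term. The comparison between groups in section 3.3 is of tissue percentages from the single biopsy, which is not a change. The only sentence that assigns a test to change names the paired tests.

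**3. The plan's own figure.** Ten per group for 1.0 mm at 80% power cannot be reproduced, because no SD is given. Solving for the SD at two-sided 0.05:

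- Two-sample, normal approximation: SD = 1.0 / [√(2/10) × (1.960 + 0.842)] = 0.80 mm.
- Two-sample, exact noncentral t on 18 df: 0.755 mm.
- Paired t within one group, 9 df: 1.00 mm.

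The stated size fits either design, so it does not settle which was meant.

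**4. Cost of the paired tests.** Inputs: n = 10 per group and two-sided alpha 0.05 from section 3.4. True loss μ and SD of change are assumed and shown as a range. The power p of one paired test comes from the noncentral t with 9 df and noncentrality μ√10/SD. Two groups are independent, so with the same true loss their verdicts disagree with probability 2p(1 − p). With different losses, both are significant with probability p₁p₂. The two-sample test of change has 18 df and noncentrality (difference/SD) × √(10/2).

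| SD of change (mm) | 0.5 | 0.755 | 1.0 | 1.5 | 2.0 |
|---|---|---|---|---|---|
| p, loss 0 | 0.050 | 0.050 | 0.050 | 0.050 | 0.050 |
| p, loss 0.5 mm | 0.803 | 0.464 | 0.293 | 0.157 | 0.109 |
| p, loss 1.0 mm | 1.000 | 0.960 | 0.803 | 0.469 | 0.293 |
| p, loss 1.5 mm | 1.000 | 1.000 | 0.987 | 0.803 | 0.562 |
| p, loss 2.0 mm | 1.000 | 1.000 | 1.000 | 0.962 | 0.803 |
| **Same true loss: verdicts disagree** | | | | | |
| both 0 | 9.5% | 9.5% | 9.5% | 9.5% | 9.5% |
| both 0.5 mm | 32% | 50% | 41% | 27% | 20% |
| both 1.0 mm | 0% | 8% | 32% | 50% | 41% |
| **Losses 1.0 mm apart: both significant** | | | | | |
| 0 and 1 mm | 5% | 5% | 4% | 2% | 1% |
| 0.5 and 1.5 mm | 80% | 46% | 29% | 13% | 6% |
| 1 and 2 mm | 100% | 96% | 80% | 45% | 24% |
| **Two-sample t, power for 1.0 mm** | 99% | 80% | 56% | 29% | 19% |

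Example at SD 0.755 and an equal loss of 0.5 mm: 2 × 0.464 × 0.536 = 0.497. A single two-sample t test has a 5% false-positive rate in every equal-loss case, and its power does not depend on where the losses lie.

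**5. Power of the proposed analysis.** Assume an SD of change of 0.755 mm, equal variances and a 1.0 mm difference. ANCOVA error variance relative to change scores is (1 + r)/2, where r is the baseline to 3-month correlation. The three-group model has 26 df with the covariate and 27 df for change scores.

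| Alpha | ANCOVA r = 0.5 | r = 0.7 | r = 0.8 | Change scores |
|---|---|---|---|---|
| 0.05/3 | 80% | 74% | 71% | 66% |
| 0.05/5 | 73% | 67% | 64% | 58% |

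The ANCOVA figures ignore chance baseline imbalance. Simulation that allows for it gives 77.9%, 72.0% and 69.3% at 0.05/3, about 2 points lower.

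**The case against.** The best defence is that a between-group comparison was intended and is nearly there. The Bonferroni sentence speaks of comparisons between treatment groups, in the same paragraph as the 1.0 mm change. The unpaired t or Wilcoxon sentence spans all three techniques and normally distributed continuous variables, and per-patient ridge change could be one of these. Calling the variables clinical characteristics may be loose wording rather than a limit.

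The reach is also limited. The unpaired test can validly compare 3-month values for Aim 1, which in a randomised trial also gives a valid, if less efficient, test of Hypothesis 1. Aim 3 and Hypothesis 2 rest on the single biopsy and are untouched. Every SD and loss in the illustration is assumed, and disagreement runs from 0% to 50%.

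Much of this stands. Between-group intent is plausible, the explicit damage falls on Aim 2, and the numbers alone cannot carry the severity. The core is not answered, though. The Bonferroni sentence names no test, the unpaired sentence does not mention change, and the sentence that does mention it prescribes the paired tests. If the intent was between-group, the written rule contradicts it.

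**Conclusion.** The concern holds and must be fixed. Followed as written, section 3.4 gives an invalid answer to Aim 2, because the tests it assigns to change cannot compare groups. That conclusion rests on the text and needs no assumed SD.

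The numerical consequence does depend on assumptions. At the SD that gives a two-sample test 80% power (0.755 mm), equal-loss groups get conflicting verdicts in 8% to 50% of trials for losses of 0 to 1.0 mm. Groups 1.0 mm apart are both significant in anything from 5% to 96%, depending on where the losses lie. Whether a real difference is masked therefore cannot be predicted from the plan. Confidence in the finding is high.

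**What to change.** Replace the paired-test sentence in section 3.4 with wording such as:

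> Change in each ridge dimension from before ridge preservation to 3 months will be compared between groups by ANCOVA of the 3-month value on treatment group and the baseline value obtained by the same method. Pairwise adjusted mean differences will be reported with confidence intervals and multiplicity-adjusted p-values for the stated number of comparisons. If the prespecified normality criterion is not met, change will be compared by pairwise Wilcoxon rank-sum tests with the same adjustment. Paired tests will describe within-group change only.

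The team should settle these details before the data are seen:

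- The number of comparisons and the adjustment method. Three groups give three pairs; the power paragraph cites five comparisons and Bonferroni.
- Which visit supplies the clinical baseline, since Table 2 marks clinical ridge assessment at both screening and Visit 1.
- The criterion for moving to the rank-sum tests.

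Speak of different rather than equivalent changes, as there is no margin. Any categorical change can use the chi-square or Fisher test already named for comparisons between groups.

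The essential step is to name a between-group test for change. A multiplicity-adjusted two-sample test of change would also be valid and is a smaller edit; ANCOVA is preferred for power.

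The cost is a wording change, a little analysis work and one model degree of freedom. No new measurements are needed, because section 3.3 and Table 2 already schedule ridge dimensions at both times. The team should know that at an SD of 0.755 mm the adjusted comparisons fall short of 80% power. This comes from the multiplicity correction the plan already invokes, and ANCOVA recovers part of the loss.

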4.0 Adverse Event Reporting

Participants will be interviewed and instructed to call if they experience any adverse events after study procedures. Such events will be recorded. In the event of a serious adverse event, the IRB will be notified per posted requirements and in full compliance with federal guidelines for research in human subjects.

5.0 Cost/Benefits to participants

5.1 Cost/Benefits to participants

There is no additional cost for study participation and study participants will pay for a reduced fee for the surgical procedures including extraction, grafting, and implant placement (\$1200). This represents a fee reduction of approximately \$800. Additionally, participants will receive a dental cleaning at no charge at the 6-month follow-up visit.

Benefits of this project for individual participants could include enhanced bone healing, due to the potential benefit of L-PRF at extraction socket grafting sites. Overall benefits include the assessment of the practicality and utility of utilizing L-PRF either alone or in combination with a bone allograft in an extraction socket model to improve new bone formation and produce a more ideal environment for the installation of dental implant(s) at an edentulous site.

5.2 Additional Dental Procedures

Study visits are not designed to take the place of routine dental care. Costs for non-study related treatment will be charged to participant account or insurance provider. Implant restorative treatments including implant abutment(s), crown(s), and/or other restorative components are not included in the reduced surgical fee for study participants.
